Project number: 2017YFC1700602

**A Multicenter, Double-blind, Randomized, Placebo-
controlled Clinical Trial of Shenbai Granules in
Reducing Recurrence of Colorectal Adenoma**

Sponsor: Affiliated Hospital of Nanjing University of Chinese Medicine

Principal investigator: [name]

Version number: 7.0

Version date: September 16, 2021

Ethical approval number: No.2018NL-067-09

Synopsis.....	3
Study visits flow chart.....	5
1. Background.....	7
2. Study objectives.....	7
3. Study design.....	7
4. Selection of subjects.....	8
5. Intervention.....	10
6. Observation indicators.....	12
7. Adverse events.....	13
8. Quality control and warranty.....	15
9. Data administration.....	16
10. Statistical analysis.....	16
11. Ethics.....	17
12. Summary and data preservation.....	18
13. Task allocation.....	18

Synopsis

Title	A multicenter, double-blind, randomized, placebo-controlled clinical trial of Shenbai Granules in reducing recurrence of colorectal adenoma
Participating units	
 1. Affiliated Hospital of Nanjing University of Chinese Medicine 2. Guangdong Provincial Hospital of Traditional Chinese Medicine 3. Longhua Hospital Affiliated to Shanghai University of Traditional Chinese Medicine 4. Shuguang Hospital Affiliated to Shanghai University of Traditional Chinese Medicine 5. the First Affiliated Hospital of Guangzhou University of Traditional Chinese Medicine 6. Affiliated Hospital of Naval Military Medical University 7. Beijing Friendship Hospital, Capital Medical University 8. the First Affiliated Hospital of Nanjing Medical University 9. Chinese Evidence-Based Medicine Center, West China Hospital, Sichuan University
Purpose	
 1. To evaluate the efficacy and safety of Shenbai Granules in reducing recurrence of colorectal adenoma 2. To provide high-quality, internationally recognized, evidence-based medical evidence for the clinical guidelines of traditional Chinese medicine in the prevention and treatment of colorectal adenoma
Design	Prospective, multicenter, double-blind, randomized, placebo-controlled clinical trial
Sample size	Total 400: Shenbai Granules group, 200; Placebo group, 200
Test Population	Patients aged 18-70 years who have undergone complete polypectomy within the recent 6 months and pathologically confirmed colorectal adenomatous polyps
Administration Plan	
Treatment group: Shenbai Granules, 1 pack/time, 2 times a day, for 6 months
 
Control group: placebos, 1 pack/time, 2 times a day, for 6 months

Effectiveness Indicators	
Primary indicator: The adenoma detection rate during follow-up for 2 years
 
Secondary indicator:
 
 (1) The detection rate of any polypoid lesions during follow-up for 2 years (2) The detection rate of high-risk adenomas during follow-up for 2 years

	(3) The detection rate of sessile serrated lesions during follow-up for 2 years
Safety indicators	
 1. Physical examination 2. Laboratory test (blood and urine routine, liver and kidney function) 3. Adverse events
Statistical Analysis	General information will be analyzed with ITT data, effectiveness with mITT and PPS data respectively, and safety with SS data.

Study visits flow chart

Study phase Project	Screening period	Treatment period			
	Baseline (-1m to 0)	Visit 1 (3m ± 1w)	Visit 2 ^a (12m ± 2w)	Visit 3 (15m ± 2w)	Visit 4 ^b (24m ± 2w)
Obtaining informed consent form	•				
Demographics	•				
Determination of inclusion and exclusion criteria	•				
Filling in general information	•				
Concomitant disease and medication before treatment	•				
Physical examinations	•	•	•	•	•
Colonoscopy and polypectomy ^c	•		•		•
Histological diagnosis	•		•		•
Boston score	•		•		•
withdrawal time	•		•		•
Blood routine	•	•	•	•	
Urine routine	•	•	•	•	
Liver function	•	•	•	•	
Renal function	•	•	•	•	
Urine pregnancy test (women)	•		•		
Distribution of trial granules	•		•		
Recovery of trial granules		•		•	
Adverse events		•	•	•	•

Concurrent medication records	•	•	•	•	•
Reason for dropouts		•	•	•	•

^a The first subsequent colonoscopy should be performed around 1 year after baseline colonoscopy.

^b The second subsequent colonoscopy should be performed around 2 years after baseline colonoscopy.

^c Each colonoscopy should have adequate bowel preparation, reach the ileocecal region and have a withdrawal time of more than 6 minutes. All polyps detected should be removed and evaluated completely.

1. Background

Colorectal cancer (CRC) is one of the most common malignant tumors that threaten human health, and its morbidity and mortality are increasing year by year. Colorectal adenoma (CRA) is the precancerous lesion of CRC. Endoscopy has become an important treatment for CRA. But endoscopic polypectomy does not reduce the recurrence and cancerization rate of adenoma. At present, measures such as increasing dietary fiber, smoking cessation, and appropriate supplementation of calcium and vitamin D are used to prevent the recurrence of CRA. However, there is no established chemopreventive agent for the prevention of recurrent CRA.

With the innovative development of the "preventive treatment for disease" theory of traditional Chinese medicine (TCM), the clinical and mechanism studies on the prevention and treatment of CRC have gradually become a research focus. Under the guidance of [name], a famous TCM master, our research team combined clinical practice to propose "accumulation of dampness and heat, deficiency of spleen and Qi" as the basic pathogenesis of CRA and established the TCM formula "Shenbai Granules (SBG)" (*Sophorae flavescens* radix, *Hedyotis diffusa*, *Codonopsis* radix, *Atractylodes macrocephalae* rhizoma, *Coicis semen*, *Coptidis* rhizoma, *Mume fructus* and *Zingiberis rhizome praeparatum*). The combination of the whole formula has the functions of beneficial Qi, invigorating spleen, clearing heat and dampness. Previous studies have found that Shenbai Granules could significantly reduce the recurrence of CRA and promote the apoptosis of colorectal cancer cells.

Therefore, we plan to conduct a multicenter, randomized, double-blind clinical study to enroll patients diagnosed with adenoma after colonoscopic resection. After obtaining informed consent, the treatment group will receive SBG, and the control group will receive SBG mimic as placebo. The efficacy and safety of SBG will be evaluated by adenoma detection rate (ADR) and adverse events, as well as clinical symptoms. This study aims to provide high-quality, internationally recognized, evidence of evidence-based medicine for the development of clinical guidelines.

2. Study objectives

The primary objective is to evaluate the efficacy and safety of SBG in reducing recurrence of CRA. The secondary objective is to provide high-quality, internationally recognized, evidence-based medical evidence for the clinical guidelines of TCM in the prevention and treatment of CRA.

3. Study design

3.1 Design guidelines

The study will be conducted in accordance with the ethical and moral principles, namely the Declaration of Helsinki, the SPIRIT Statement, as well as the principles of scientificity, the principles of Good Clinical Practice and current laws and regulations.

3.2 Study type

A multicenter, randomized, double-blind, placebo-controlled clinical trial design is adopted.

3.3 Sample size

According to the literature search and previous research results, the average detection rate of recurrent adenomas without agent intervention for patients after polypectomy is 52%. We hope that ADR will be reduced by 34% after intervention of SBG. With a significance level (alpha) of 5% and power of 90%, the patient number needed is 160 in each group. Allowing for 20% of participants to drop out, the target number of participants to be randomly assigned is 400.

3.4 Randomization method

The stratified block randomization method is used, and the following design is completed by an independent third-party organization.

- (1) Design and specify the block length;
- (2) Generate the block number and random numbers within the block, and conduct one-to-one correspondence between the random numbers with the trial granules number;
- (3) Allocate the cases to the treatment and placebo groups within the block in a 1:1 ratio, and finally obtain the result of block randomization; and generate the randomization list and blinding codes.

3.5 Blinding procedures

A double-blind design is used in this study for the investigators and subjects. The blinding codes are separately sealed and stored by the independent third-party organization. Trial granules are randomly coded as subject unique identification codes, and used by each clinical site according to the assigned drug numbers and in the order of case enrollment. Clinical monitors and investigators must be blinded at all times.

3.6 Control selection

Since there is no internationally recognized standard treatment for the prevention and treatment of CRA, we chose the SBG mimic as a control drug.

4.1 Diagnostic criteria

The criteria are established according to the *Integrated colorectal Oncology*:

Colorectal adenoma (CRA): Colonoscopy reveals colonic and (or) rectal polyps, and pathological diagnosis is adenomatous polyps, including tubular adenoma, villous adenoma, and tubulovillous adenoma.

Tubular adenoma (microscopically): Adenoma is mainly composed of mucin-secreting epithelium with varying degrees of dysplasia. The epithelium is tall columnar and arranges in a glandular tubular structure, which is separated by the lamina propria stroma. The glands are generally more regular, sometimes also can appear different degrees of branching and irregular shape. The nuclei of the epithelial cells are large and hyperchromatic, and the nuclei are pen-rod shaped and closely arranged. In mild atypia, the nuclei are arranged at the base of the epithelium, and with the increase of atypia, the nuclei shift upward to form pseudostratified structures.

Villous adenoma (microscopically): The villi are branching and growing vertically to the mucosa, the center of the villi is a central cord, and there is fibrovascular stroma. The surface epithelium is the same as that of tubular adenoma, but the general atypia is more obvious.

Tubulovillous adenoma (microscopically): The tumor tissue is composed of a mixture of glandular tubular, papillary or villous structures, of which villous or papillary structures account for 1/5-4/5 of adenomas. If the villous structure comprises less than 1/5 or more than 4/5 of the adenoma, it is

classified as tubular or villous, respectively.

[Reference]

[1] Jingyuan Fang. Integrated colorectal Oncology [M]. Beijing: People's Medical Press,2015,205-206.

4.2 Inclusion criteria

- (1) Patients underwent colonoscopy within the last 6 months, and all polyps detected have been removed;
- (2) Meet the diagnostic criteria for CRA;
- (3) Between 18 and 70 years of age (inclusive);
- (4) Those who have been fully informed and signed the informed consent.

4.3 Exclusion criteria

- (1) Colonoscopy suggests poor cleanliness and the Boston score is less than 6, or it is no cecal intubation, or withdrawal time is less than 6 minutes;
- (2) Patients with hereditary polyposis such as familial adenomatous polyposis, MUTYH-associated polyposis, Peutz-Jeghers syndrome, serrated polyposis syndrome, etc;
- (3) There is reliable evidence that the tumor has invaded the muscularis propria mucosa, or deep submucosal invasion is suspected;
- (4) Combined with colorectal malignant tumor or previous history of colorectal malignant tumor;
- (5) Colonoscopy is highly suggestive of inflammatory bowel disease;
- (6) Pregnant and lactating women;
- (7) Women of appropriate age who have recently planned to have children;
- (8) Unstable vital signs, or severe heart, lung, cerebrovascular disease, or liver and kidney dysfunction (ALT, AST > 2 × upper limit of normal; Serum creatinine and blood urea nitrogen > 1.5 × upper limit of normal) who can not tolerate colonoscopy and clinical intervention;
- (9) Loss of follow-up due to frequent changes in work environment or other circumstances;
- (10) Chemopreventive drugs (aspirin, folic acid, vitamin D, calcium, etc.) with potential for the treatment of colorectal adenoma have been used;
- (11) Patients participating in other clinical trials.

4.4 Withdrawal criteria

- (1) If the patient has severe gastrointestinal symptoms during the study period, the study can be stopped according to the investigator's judgment. Or if the patient's colonoscopy showed deterioration of intestinal polyps, the study can be stopped, and the ineffective case can be treated.
- (2) The adverse drug reactions have occurred during the study, or other serious adverse events, according to the judge to stop the case of clinical studies.
- (3) Significant deviation has come up in the implementation of study protocol, such as poor adherence, difficult to evaluate drug effect.
- (4) The patient is unwilling to continue the clinical trial, and offer to withdraw from the trial to the doctor in charge.

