4.5 Dropout and management of cases

Dropout cases are defined as all the subjects who had completed the informed consent form and are screened and qualified to enter the randomized trial, regardless of when or for reasons, but have not completed the observation period specified by the study.

When the subjects drop out, the researchers should contact the subjects as much as possible by visiting their home, making follow-up appointments, telephone calls, and letters to ask the reasons, record the time of the last medication, and complete the evaluation items that can be completed.

For patients who withdraw from the study due to adverse events or ineffective treatment during the study, researchers should take corresponding measures according to the actual situation of patients.

The study data of the dropped cases should be properly preserved, not only for archival purposes, but also for the statistics of the full analysis set. No additional information is required for drop-out patients.

5. Intervention

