10.2 Selection of data sets for analysis

Full Analysis Set (FAS) refers to the ideal set of participants approaching as closely as possible to the analytic principle of intentionality (including all the cases randomized into the group, receiving at least one treatment of trial medicines, and having the evaluating data after administration). The missing data of the efficacy index in the visiting period will be supplemented with the method of Last Observation Carry Forward (LOCF).

Per Protocol Set (PPS) refers to the set of participants who meet the inclusion criteria in the trial treatment protocol, have good compliance, have not used the combined medicines that seriously affect the evaluation of efficacy, and not tremendously violated the trial protocol.

Safety Analysis Set (SS) refers to all cases that received at least one treatment with trial medicines after randomization, and had the data for safety evaluation post administration.

The division of statistical analytic dataset will be finalized in the conference of data review.

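### Sections 4.4 and 4.5 do not separate stopping the granules from leaving follow-up, and nothing requires the year-1 and year-2 colonoscopies after withdrawal, so primary outcomes can be lost selectively

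*Combined protocol and SAP*

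**What the plan says.** Section 4.4 gives four grounds for withdrawal: severe gastrointestinal symptoms or worsening polyps, adverse reactions or serious adverse events, major deviation, and the patient's own wish. All are worded as ending the study or trial, none as stopping the granules alone. On polyps it says "if the patient's colonoscopy showed deterioration of intestinal polyps, the study can be stopped". On adherence it says "Significant deviation has come up in the implementation of study protocol, such as poor adherence, difficult to evaluate drug effect".

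Section 4.5 defines a dropout as anyone randomised, "regardless of when or for reasons, but have not completed the observation period specified by the study". Staff should "contact the subjects as much as possible by visiting their home, making follow-up appointments, telephone calls, and letters to ask the reasons", record the last medication and "complete the evaluation items that can be completed". The section closes with "No additional information is required for drop-out patients".

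Section 6.2 and the flow chart schedule colonoscopy at about 1 and 2 years after the baseline examination. They do not say what happens after withdrawal. The 6.2 denominator is every case in the group. Section 10.2 limits the full analysis set (FAS) to treated participants "having the evaluating data after administration", and adds: "The missing data of the efficacy index in the visiting period will be supplemented with the method of Last Observation Carry Forward (LOCF)". The synopsis names mITT for effectiveness, which 10.2 does not define. Section 10.1 leaves the SAP to be written after study start and settled before database lock.

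**The concern.** The endpoint is seen only at colonoscopy. If stopping the granules is taken as leaving the study, the participant may have no further colonoscopy, and the reason for stopping may be related to arm or to risk. Blinding and a matched placebo limit decisions made with knowledge of the arm. They do not prevent the arms from differing in tolerability or adherence. At stake is a comparison that no longer rests on everyone randomised, with part of the outcome unrecoverable.

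The schedule gives no reason for this loss. Granules are taken for three months in each year (5.3) and recovered at months 3 and 15, while the colonoscopies fall at months 12 and 24. A fully adherent participant is off granules for most of follow-up, so stopping early does not in itself stand in the way of the examination.

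**Working it through.** **The plan's own figure.** Section 3.3 gives 52% without treatment, a 34% reduction, alpha 5%, power 90%, 160 per arm, 20% dropout and 400 in total. Read as relative, the reduction gives 0.52 × 0.66 = 0.3432, a difference of 0.1768. The unpooled two-sided formula is n = (1.960 + 1.282)² × (0.52×0.48 + 0.3432×0.6568) / 0.1768² = 159.7, so 160. Then 160/0.8 = 200 per arm. The sample size reproduces; the issue is outcome retention.

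**What happens to a withdrawn participant under the text**

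- Adenoma found before withdrawal: already an event, nothing lost.
- Clear year-1 colonoscopy, no year-2 colonoscopy (for example stopped at the month-15 drug count): LOCF codes the person adenoma-free at 2 years.
- No follow-up colonoscopy (for example stopped at month 3): not settled. The FAS condition may exclude the person; the literal 6.2 denominator counts the person as adenoma-free; LOCF from baseline can be read either way, because an adenoma was found at baseline and then removed.

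**Illustration with no true effect.** True rate 52% in both arms, 200 per arm, two-sided 5% test of two proportions with pooled variance under the null. Let w be the share withdrawn, r their true risk and f the share of events seen by year 1. All three are assumptions. Main case: w = 15% SBG, 5% placebo. Differences are SBG minus placebo; a negative value looks like benefit.

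| Handling | Formula for the rate | SBG vs placebo | Difference (points) | Type I error |
|---|---|---|---|---|
| Excluded, r = 65% | (0.52 − w·r)/(1 − w), n = 170 vs 190 | 0.497 vs 0.513 | −1.6 | 6.1% |
| Excluded, r = 52% | same | 0.520 vs 0.520 | 0 | 5.0% |
| Excluded, r = 40% | same | 0.541 vs 0.526 | +1.5 | 5.9% |
| Year 2 lost, LOCF, f = 30% | 0.52·(1 − w(1 − f)), n = 200 | 0.465 vs 0.502 | −3.6 | 11.2% |
| Year 2 lost, LOCF, f = 50% | same | 0.481 vs 0.507 | −2.6 | 8.1% |
| Year 2 lost, LOCF, f = 70% | same | 0.497 vs 0.512 | −1.6 | 6.1% |
| All lost before year 1, coded free | 0.52·(1 − w) | 0.442 vs 0.494 | −5.2 | 18.0% |
| All lost before year 1, coded positive | 0.52 + 0.48·w | 0.592 vs 0.544 | +4.8 | 16.2% |

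If half are excluded before year 1 (r = 52%) and half are lost after year 1 with LOCF (n = 185 vs 195), the difference is −2.0, −1.4 or −0.9 points and type I error 6.8%, 5.9% or 5.3% for f = 30%, 50% or 70%.

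Milder split, 12% vs 8%: exclusion gives 5.2% (r = 65%, −0.6 points) or 5.1% (r = 40%, +0.6 points); year-2-only loss with LOCF gives 6.0%, 5.5% or 5.2%; all coded adenoma-free gives 7.0%. Swapping the arms reverses every sign.

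**Planned effect, equal 20% loss in both arms** (52% vs 34.3%, 17.7 points):

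| Handling | Difference (points) | Power |
|---|---|---|
| All 200 per arm observed | 17.7 | 94.9% |
| Excluded, 160 per arm | 17.7 | 89.5% |
| Year 2 lost, LOCF, f = 30%, 50%, 70% | 15.2, 15.9, 16.6 | 88.5%, 90.7%, 92.6% |
| All coded adenoma-free (0.416 vs 0.275) | 14.1 | 84.8% |
| All coded positive (0.616 vs 0.475) | 14.1 | 81.3% |

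**The case against.** Section 4.5 does direct staff to pursue dropouts and finish what can be finished, and colonoscopy is the main evaluation item. Section 6.2 and the flow chart set both colonoscopies from the baseline examination, with no condition on taking granules. Section 8.2 treats compliance outside 80–120% as a major violation and 10.2 makes good compliance a condition for the per protocol set (PPS), so some poor adherers will probably stay in follow-up. This is why the text is ambiguous rather than prohibitive. But the best-effort clause names no colonoscopy and no time point, it is undercut by the closing sentence of the same section, and 4.4 still allows poor adherence to end participation.

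The largest illustrative figures come from coding, which a SAP can still settle. That is correct. Exclusion, which best isolates the missing examinations, gives at most 6.1% at 15% vs 5% and about 5.2% at 12% vs 8%. No section supports a threefold difference between arms, so that split is a stress case.

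Power is not the issue: the plan already allows 20% loss, and 89.5% is essentially the stated 90%. Worsening polyps need not cost an outcome either, since an adenoma already found counts. Both points stand and narrow the concern to bias from loss before year 1 or after a clear year-1 result. They do not supply the missing requirement.

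**Conclusion.** The concern holds. The protocol does not separate treatment discontinuation from the end of follow-up, does not expressly require outcome colonoscopies after withdrawal, and gives two statements in 4.5 that must be reconciled. As written, 10.2 also turns a clear year-1 result with no year-2 examination into an adenoma-free 2-year outcome.

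Selective loss is a risk, not a demonstrated fact. Its size and direction cannot be determined from the documents. Under the assumed splits, type I error ranges from nominal to 18%: near nominal when withdrawal is almost balanced or those lost carry average risk and are excluded, and highest when everyone lost before year 1 is coded one way. The planned 20% loss is 40 of 200 per arm, so some loss is expected. The protocol should be amended; confidence in the importance of the point is medium.

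**What to change.** - **4.4 and 4.5:** record stopping the granules as treatment discontinuation, separate from withdrawal of consent to follow-up. When treatment is stopped stays with the investigators and is not changed. Unless consent to follow-up is withdrawn or the examination cannot be done, collect the already scheduled year-1 and year-2 colonoscopy results and analyse by randomised arm. Poor adherence should not end follow-up; it stays a PPS criterion. Delete "No additional information is required for drop-out patients".
- **6.2 and 10.2:** do not use LOCF for the adenoma outcome. An adenoma at any follow-up colonoscopy is an event. No follow-up colonoscopy, or a clear year 1 without year 2, is a missing 2-year outcome. Multiple imputation using the year-1 result where there is one is a reasonable choice, with a tipping-point analysis varying the assumed risk by arm.

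**Cost.** An amendment, which 11.1 sends back to the ethics committee, and some retention effort. Sections 8.2 and 11.2 say study examinations are paid for; confirm that this covers participants who have stopped the granules. Examinations already missed stay missing.

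The estimate may be less favourable, because off-treatment participants count. If half of the 20% loss is retrieved (20 per arm, 180 analysed), the SBG rate is (160 × 0.3432 + 20 × p)/180, where p is the rate in those retrieved. With full, half or no effect in them it is 0.343, 0.353 or 0.363, and power is 92.6%, 89.5% or 85.4%, against 89.5% at 160 per arm. The gain is less bias, not reliably more power.
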